6.7 DOSE MODIFICATION

Dose modification is not foreseen in this study. Treatment might need to be interrupted or permanently discontinued if deemed necessary due to an AE (Section 7 and Section 8.3).

6.8 INTERVENTION AFTER THE END OF THE STUDY

After the end of this study, participants who complete the IMP treatment (double-blind or open-label SAR442168 if meeting 6-month CDP) may be offered the option to participate in an LTS study for an additional 2 years, or until SAR442168 is approved in their respective country, whichever comes first. Details of the LTS study will be described in a separate protocol.

Amended Clinical Trial Protocol 12 SAR442168-EFC16645 - tolebrutinib 20-Dec-2023 Version number: 1

7 DISCONTINUATION OF STUDY INTERVENTION AND PARTICIPANT DISCONTINUATION/WITHDRAWAL

7.1 DISCONTINUATION OF STUDY INTERVENTION

7.1.1 Definitive discontinuation

The study intervention should be continued whenever possible.

Permanent intervention discontinuation is any treatment discontinuation associated with the definitive decision by the Investigator or the participant not to re-expose the participant to the study intervention at any time.

In rare instances, it may be necessary for a participant to permanently discontinue the study intervention. If study intervention is permanently discontinued, the participant will be asked to remain in the study to be evaluated until the EOS visit. For this set of participants (participants who discontinued the IMP and/or switched to other DMTs), no PK or biomarker samples will be collected after the pEOT visit, and MRI assessments will be performed only annually using the next annual visit as the starting point.

This will be important to continue to evaluate for safety and efficacy. See the SoA (Section 1.3) for data to be collected at the time of discontinuation of the study intervention. In the case that the study intervention is permanently discontinued, the participant should be treated for MS according to local clinical practice and the best judgment of the Investigator.

The following may be justifiable reasons for the Investigator or Sponsor to discontinue a participant from treatment:

- Adverse events that endanger the safety of the participant, or if discontinuation of study intervention is desired or considered necessary by the Investigator and/or participant.
- If IMP discontinuation criteria are met as per the guidance for the follow up of laboratory abnormalities (Appendix 2 [Section 10.2]).
- The participant is no longer deriving a therapeutic/clinical benefit in the opinion of the Investigator.
- If a female participant becomes pregnant or wishes to become pregnant during the study.
- At participant's request, ie, withdrawal of the consent for treatment.
- Any serious opportunistic infections (eg, PML [see Appendix 6 {Section 10.6}], HIV)
- Continued need for/chronic use of prohibited a concomitant medication (see Appendix 9 [Section 10.9]).
- Use of open-label SAR442168 or non-study disease modifying therapy approved for NRSPMS in their respective countries (eg, after 6-month CDP).

Discontinuation of study intervention for abnormal liver function is required by the Investigator when a participant meets one of the conditions outlined in the algorithm (Appendix 6 [Section 10.6]) or if the Investigator believes that it is in best interest of the participant.

Any clinically significant abnormal laboratory value or ECG parameter will be rechecked for confirmation after 24 hours before making a decision of definitive discontinuation of the IMP for the concerned participant.

If a clinically significant finding is identified in the ECG (including, but not limited to changes from baseline in QT interval corrected using Fridericia's formula [QTcF]) after enrollment, the Investigator or qualified designee will determine if the participant can continue in the study and if any change in participant management is needed. Review of ECG findings by a cardiologist may be considered for a decision of a definitive discontinuation of study intervention because of ECG changes. This review of the ECG printed at the time of collection must be documented. Any new clinically relevant finding should be reported as an AE.

See the SoA (Section 1.3) for data to be collected at the time of intervention discontinuation and follow-up and for any further evaluations that need to be completed.

Handling of participants after definitive intervention discontinuation

Participants will be followed according to the study procedures specified in this protocol:

- Up to the scheduled date of study completion, or,
- Up to recovery or stabilization of any AE to be followed as specified in this protocol, whichever comes last.

The participant should be treated for MS according to local clinical practice and the best judgement of the Treating Investigator.

If possible, and after the definitive discontinuation of study drug, the participants will be assessed using the procedures planned for the pEOT visit, including collection of a PK sample if the pEOT visit can be scheduled within a maximum of 24 hours after the last IMP dose. Participants will be asked to continue in the study, attending all scheduled visits per SoA (Section 1.3), if possible until the end of the study. If the participant does not agree to the full visit schedule after a decision for permanent end of treatment, a reduced visit schedule may be agreed with the participant. Every effort should be made to collect endpoint information and vital status at least once a year and at the end of study.

For participants with definitive discontinuation of study drug who do not agree to remain in the study after the premature end of treatment visit, if the premature end of treatment visit is less than 3 weeks after the last dose of the study drug, an additional visit should be performed with assessments normally planned for the follow-up visit.

Participants who are treated with open label IMP who decide to prematurely and permanently discontinue the open label IMP prior to the common study end date should be assessed as soon as possible using the procedures normally planned for the premature end of treatment visit. Participants who prematurely and permanently discontinue open label IMP who do not agree to

remain in the study after performing a visit analogous to the premature end of treatment visit, should have an additional visit performed with assessments normally planned for the follow-up visit if the last study visit was less than 3 weeks after the last dose of the open label IMP.

Participants who prematurely and permanently end treatment for a reason other than 6-month CDP will not be eligible for open-label IMP.

All cases of definitive study drug discontinuation must be recorded by the Treating Investigator in the appropriate pages of the eCRF when considered as confirmed.

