a Screening period can range from D-28 to D-1; Randomization visit can be performed only once IMPs are available at site. The interval between screening and randomization visits can range from 11 days (minimum) to 28 days (maximum). However, if required, the randomization visit can be performed earlier than 11 days upon IMP receipt at the site, assuming the participant is eligible for randomization. In case of any delay to screening (MRI rescheduling, lab retests, etc), an additional period of up to 2 weeks is allowed.

b From D1 to EOS, unscheduled visits may be performed at any time by the Investigator (eg, for evaluation of an adverse event). Assessments may be done on as needed basis to evaluate the participant in accordance with the Investigator's best judgement and in-line with the study protocol. At a minimum, a physical examination should be performed, and body temperature and vital signs should be measured.

Amended Clinical Trial Protocol 12	
SAR442168-EFC16645 - tolebrutinib	

- c At the EOS, the participants who have completed treatment with IMP (double blind or open label if meeting CDP) may be offered participation in LTS study. Follow-up visit assessment only performed for those participants who completed treatment and are not willing to take part in the LTS study. For other situations where a follow-up visit is needed, please see Section 7.1 and the Study Manual.
- *d* These visits may be done as home health visits (where applicable) or onsite visits (it is preferable that tests are performed at the central laboratory). In any situations where this is not possible (to be documented in source documents), the tests for these visits may be performed at a local laboratory.
- e If a participant prematurely permanently discontinues treatment with IMP, the participant will undergo pEOT visit as soon as possible. A PK sample should also be collected if the pEOT visit can be scheduled within a maximum 24 hours after the last IMP dose. Participants will then be asked to continue with the study visits as scheduled until the common EOS Visit is reached. During these visits, all study procedures/assessments will be performed except IMP administration and blood sampling for PK and biomarkers (NfL, Chi3L1, and Ig levels). MRI scans for these participants will only be performed annually (using the next annual visit as the starting point). Additional information is provided in the Study Manual.

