6.6.1 Open-label treatment

If a participant achieves the primary endpoint (6-month CDP), they may, in conjunction with the Treating Investigator, choose to receive one of the following:

- 1. To switch to open-label SAR442168 treatment; OR
- 2. To switch to a non-study treatment approved for NRSPMS in their respective country. In this case, the participant will permanently discontinue the IMP and will be encouraged to remain in the study for planned clinical visits (see Section 7.1.1) until common study end.

In case the participant switches to open-label SAR442168 treatment, he/she will need to be monitored for liver function tests after the first open-label dose at Weeks 2, 3, 4, 5, 6, 7, 8, 9, 10, 11, and 12, and then monthly for the next 9 months. After that, the schedule visits timepoints per SoA will be resumed (ie, every 3 months), until the common study end. Whenever a timepoint will coincide with a scheduled visit as per SoA (Section 1.3), the full scheduled visit assessments will be performed instead of the liver monitoring testing alone.

For participants achieving 6-month CDP, the Investigator must ensure that the participant does not meet any of the following criteria prior to the switch to open-label SAR442168 treatment:

• Current alcohol intake >2 drinks per day for men and >1 drink per day for women (1 drink = approximately 14 grams of alcohol = 350 mL beer = 140 mL wine = 40 mL of spirits).

- Acute liver disease, cirrhosis, chronic liver disease (unless considered stable for >6 months).
- Confirmed ALT >1.5 × ULN OR AST >1.5 × ULN OR ALP >2 × ULN (unless caused by non-liver-related disorder or explained by a stable chronic liver disorder) OR total bilirubin >1.5 × ULN (unless due to Gilbert syndrome or non-liver-related disorder).

Liver function tests will be performed for all participants prior to the start of open-label treatment.

Should the participant and Investigator opt for the provision of open-label medicine, they will remain blinded to the original treatment assignment.

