#### Table 1 - Objectives and endpoints

	Objectives	Endpoints		
Secor	ndary			
•	To evaluate efficacy of tolebrutinib compared to placebo on clinical endpoints, MRI lesions, cognitive	• Time to onset of sustained 20% increase in the 9-HPT for at least 3 months		
	performance, physical function, and quality of life	
 
Time to onset of sustained 20% increase in the T25-FW for at least 3 months
 
		
		
 
Time to onset of 3-month CDP as assessed by the EDSS score
 
		
		
 
Total number of new and/or enlarging T2-hyperintense lesions as detected by MRI, defined as the sum of the individual number of new and/or enlarging T2 lesions at all scheduled visits starting after baseline up to and including the EOS visit
 
		
		
 
Time to onset of CDI defined as a ≥1.0 point decrease on the EDSS score from baseline confirmed over at least 6 months
 
		
		
 
Percent change in brain volume loss (BVL) as detected by MRI scans at the EOS compared to Month 6
 
		
		
 
Change in cognitive function at the EOS compared to baseline as assessed by SDMT
 
		
		
 
Change in cognitive function at the EOS compared to baseline as assessed by CVLT-II, where available
 
		
		
 
Change in MSQoL-54 questionnaire score from baseline through the EOS
 
		
•	To evaluate safety and tolerability of tolebrutinib	
 
Adverse events (AEs), serious AEs, AEs leading to permanent study intervention discontinuation, AEs of special interest, and potentially clinically significant abnormalities in laboratory tests, safety scales, ECG, and vital signs during the study period
 
		
•	To evaluate population pharmacokinetics of tolebrutinib and relevant metabolite(s) in NRSPMS and its relationship to efficacy and safety	
 
Plasma concentration of tolebrutinib and relevant metabolite(s) (population PK assessment) at Months 6, 9, and 12
 
		
•	To evaluate pharmacodynamics (PD) of tolebrutinib	
 
Change in plasma NfL levels at the EOS compared to baseline
 
		
		
 
Change in lymphocyte phenotype subsets in whole blood at the EOS compared to baseline in a subset of participants
 
		
		
 
Change in serum immunoglobulin level at baseline compared to the EOS
 
		
		
 
Change in serum Chi3L1 levels at baseline compared to the EOS
 
		

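### Protocol 7.1.1 lists open-label SAR442168 as a reason for definitive discontinuation while 4.1, 6.6.1, 6.8 and SoA footnote c treat it as continuing IMP, so biomarker sampling after the switch is left unclear

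*Protocol*

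**What the plan says.** **Text that groups the switch with discontinuation.** Under its heading on definitive discontinuation, Protocol 7.1.1 introduces a list with "The following may be justifiable reasons for the Investigator or Sponsor to discontinue a participant from treatment". The last item is "Use of open-label SAR442168 or non-study disease modifying therapy approved for NRSPMS in their respective countries (eg, after 6-month CDP". Later in 7.1.1, people who end treatment prematurely and permanently for any reason other than 6-month CDP are made ineligible for open-label IMP. This implies that a switch after 6-month CDP is itself a premature, permanent end of treatment.

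**Text that treats the switch as continuing IMP.** Section 6.6.1 offers two options after 6-month CDP. Only for the second, a non-study treatment, does it add: "In this case, the participant will permanently discontinue the IMP and will be encouraged to remain in the study". For the first, open-label SAR442168, it prescribes extra liver tests and then a return to the SoA visits until the common study end. Section 6.8 refers to "participants who complete the IMP treatment (double-blind or open-label SAR442168 if meeting 6-month CDP" as those who may enter the long-term study, and SoA footnote c refers to "the participants who have completed treatment with IMP (double blind or open label if meeting CDP". Section 4.1 likewise counts open-label drug as IMP treatment that can be completed.

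**The sampling rule.** For participants who discontinued the IMP and/or moved to other DMTs, 7.1.1 says "no PK or biomarker samples will be collected after the pEOT visit, and MRI assessments will be performed only annually". Section 8.6 stops NfL, Chi3L1 and Ig collection for a group described in nearly the same way. SoA footnote e stops the same samples after premature permanent discontinuation of IMP.

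**The endpoints.** SAP Table 1 lists "Change in plasma NfL levels at the EOS compared to baseline" as a secondary endpoint, with matching entries for Chi3L1 and immunoglobulins.

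**The concern.** A site reading the 7.1.1 list, the eligibility sentence and footnote e together could send an open-label switcher down the premature-end-of-treatment path and draw no further biomarker samples. A site reading 6.6.1, 6.8 and footnote c would carry on with the SoA schedule. Both are following the protocol.

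Under the first reading, the end-of-study NfL, Chi3L1 and Ig samples are absent only in people who progressed and switched. The missingness then depends on the primary outcome, and probably differs by arm because a larger proportion of placebo participants is expected to progress. The participants left in the end-of-study summary would be enriched for non-progressors, more so on placebo. If sites divide on the reading, the missingness also follows site. Samples that were never drawn cannot be recovered at analysis.

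**Working it through.** **1. The passages side by side**

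| Place | Status of open-label SAR442168 |
|---|---|
| 7.1.1, list of reasons | Grouped with non-study DMTs as a reason to discontinue |
| 7.1.1, eligibility sentence | Implies that the 6-month-CDP switch ends treatment permanently |
| 7.1.1, definition | Discontinuation is a decision "not to re-expose the participant to the study intervention at any time", which a switch to active study drug does not fit |
| 7.1.1, open-label paragraph | Calls it IMP; a visit of the pEOT type is due when it is stopped |
| 7.1.1 and 8.6, sampling stop | Covers those who discontinued the IMP or went to other DMTs; open-label drug not named |
| SoA footnote e | Stop follows premature permanent discontinuation; later visits have no IMP administration; open-label drug not named |
| 4.1, 6.6.1, 6.8, footnote c | Continuing IMP |
| SAP 5.5 | Carves the switch out of time to study intervention discontinuation |

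The status is contradictory, and no sampling-stop passage settles whether switchers are covered.

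**2. What is lost if the stop is applied to switchers**

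SoA schedules: NfL and Chi3L1 at Day 1, Months 3, 6, 12 and 24, then yearly, plus pEOT and EOS. Ig is the same without Month 3. MRI at screening, Months 6, 12, 18 and 24, then yearly, plus pEOT and EOS.

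| Switch at | NfL, Chi3L1 and Ig lost | Scheduled MRI lost |
|---|---|---|
| Month 9 | 12, 24, 36, 48, EOS | 18 |
| Month 12 or 15 | 24, 36, 48, EOS | 18 |
| Month 18 or 21 | 24, 36, 48, EOS | none |
| Month 24 or 30 | 36, 48, EOS | none |

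A pEOT visit carries its own biomarker samples and MRI, so a value near the switch would exist. The end-of-study biomarker value would not.

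**3. Ceiling on the number affected**

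Inputs from Protocol 9.2 and SAP Section 4: 288 events, HR 0.70, 2:1 allocation, 1290 randomised (430 and 860), 2-year placebo event rate 23.6%, 10% annual discontinuation, 24 months' enrolment and 24 months' minimum follow-up. Uniform accrual is my assumption.

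Check on the plan's figure (Schoenfeld): √(288 × 1/3 × 2/3) × |ln 0.70| − 1.96 = 8 × 0.3567 − 1.96 = 0.893, giving 81.4% power, in line with the stated 80%.

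Hazards per year:
- placebo λ = −ln(1 − 0.236)/2 = 0.1346
- tolebrutinib λ = 0.70 × 0.1346 = 0.0942
- discontinuation = −ln(0.90) = 0.1054

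With h = λ + 0.1054, expected events per arm = n × (λ/h) × [1 − (e^(−2h) − e^(−4h))/(2h)].
- Placebo: h = 0.2400; 430 × 0.5609 × (1 − 0.4915) = 122.6
- Tolebrutinib: h = 0.1996; 860 × 0.4721 × (1 − 0.5532) = 181.4
- Total about 304

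Scaled to 288 (factor 288/304.1 = 0.947): 116/430 = 27% of placebo and 172/860 = 20% of tolebrutinib; overall 288/1290 = 22%. At 50% uptake these halve.

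The plan also allows about 1100 participants with about 30 months' minimum follow-up. The same formula, with exponents −2.5h and −4.5h, gives 289 events. Scaled to 288, that is 116/367 = 32% and 172/733 = 24%.

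**4. Ceiling on the Month 18 MRI**

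To switch before Month 18, 6-month CDP must be confirmed by about Month 15, so onset must fall by about Month 9 (252 days = 0.690 year). Expected onsets n × (λ/h) × (1 − e^(−0.690h)) are 36.8 on placebo and 52.2 on tolebrutinib. Their sum, 89, is 29% of 304. At most about 29% of progressors could lose that scan, and only if they switch.

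**The case against.** The strongest reply is that the protocol, read as a whole, points away from the harmful reading. The 7.1.1 list gives reasons that may justify stopping, not mandatory ones. Its definition of permanent discontinuation requires no re-exposure to study intervention. The sampling stop speaks of other DMTs, and open-label SAR442168 is not one. Footnote e describes visits without IMP. Section 6.6.1 sends open-label participants back to the SoA and calls for the full scheduled assessments when a liver test coincides with a scheduled visit. The SAP expects MRI and functional data after the switch, since 3.3.1.2.3 plans sensitivity analyses excluding them. Footnote e also defers to a Study Manual that is not available here.

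Most of this stands, and it makes the loss possible rather than certain. It does not remove the ambiguity. Having discontinued the IMP is enough by itself to trigger the stop, and the 7.1.1 list and eligibility sentence supply a basis for putting switchers in that group.

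Stronger readings are tempting, and the documents do not support them:
- **That 7.1.1 compels sites to stop sampling at the switch.** It does not, for the reasons just given.
- **That MRI follow-up is broadly cut.** At most one scheduled scan is lost; from Month 18 the SoA schedule and an annual one coincide.
- **That NEDA-3 is harmed.** NEDA-3 requires absence of 6-month CDP (Protocol 8.1.7.2), so these switchers have already failed it.
- **That more placebo than tolebrutinib participants are affected.** Only the proportion is higher on placebo; the counts are 116 and 172.
- **That a confirmatory result is at risk.** SAP 3.7.2 summarises these biomarkers descriptively, and they are outside the hierarchy in SAP 3.5.

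**Conclusion.** The contradiction is real, and the biomarker schedule after an open-label switch is not stated unambiguously. The consequence is conditional. Where a site applies the 7.1.1 stop to switchers, end-of-study NfL, Chi3L1 and Ig are lost selectively in participants who met the primary endpoint and switched.

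The ceiling is about 27% of placebo and 20% of tolebrutinib participants at 1290 randomised, or 32% and 24% at the reduced size of about 1100. It assumes constant hazards, uniform accrual, every progressor switching, and every site reading the text that way. The true share must be lower: Section 6.6.1 lets progressors stay on double-blind treatment, sets liver and alcohol conditions and leaves supply to the country level, and those confirmed near study end have little time to switch. The documents give no uptake figure.

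The primary endpoint and power are untouched, because the event precedes the switch and EDSS visits continue on either reading. The only MRI effect is a possible missing Month 18 scan, which bears on the exploratory Month 18 T2 lesion volume. This is a clarification worth making because it changes what is collected for named secondary endpoints.

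**What to change.** **Protocol.** Reconcile the 7.1.1 list, definition, sampling rule and eligibility sentence with 4.1, 6.6.1, 6.8, 8.6 and SoA footnotes c and e. State whether IMP discontinuation in the sampling rules means the end of double-blind treatment or the end of all SAR442168, and state explicitly which biomarker and MRI schedule applies after an open-label switch. This concerns assessments only and should not alter who switches or who stops treatment.

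**SAP 3.7.2.** Summarise end-of-study NfL, Chi3L1 and Ig by randomised arm, with and without post-switch samples. The section now groups by actual treatment. Add a note that the version without post-switch samples is selected on progression, and that the version with them includes tolebrutinib exposure in former placebo participants. Report, by arm, how many switchers have an end-of-study sample.

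**Cost.** A clarification letter or amendment and one additional table. The samples and scans are already in the SoA. Samples already missed cannot be replaced, so the protocol clarification is useful only while participants are still being followed; the SAP display is useful in either case.
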